4 STATISTICAL METHODS

4.1 Quality Control

All tables, figures and listings planned in this SAP will undergo quality control in accordance with Parexel's Standard Operating Procedures (SOPs).

4.2 General Presentation Considerations

4.2.1 General Continuous Data Presentation

Continuous data will be summarized in terms of the mean, standard deviation (SD), coefficient of variation as appropriate, median, minimum, maximum and number of non-missing observations, unless otherwise stated. Continuous data that are expected to be skewed will be presented in terms of the maximum, upper quartile, median, lower quartile, minimum and number of observations.

Minimum and maximum will be reported to the same number of decimal places as the raw data recorded in the database. Mean, median, lower quartile and upper quartile will be reported to one more decimal place than the raw data recorded in the database. SD will be reported to two more decimal places than the raw data recorded in the database. In general, the maximum number of decimal places reported shall be four for any summary statistic.

4.2.2 General Categorical Data Presentation

Categorical data will be summarized in terms of the number of subjects providing data at the relevant time point (n), frequency counts and percentages.

Percentages will be presented to one decimal place. Percentages will be calculated using 'n' (the total number of subjects providing data at the relevant time point) as the denominator.

4.2.3 Study Day and Study Week

Study Day (in days) will be calculated from date of randomization, and it will be used to show start and stop day of assessments or events.

For visit (or event) prior to randomization,

Study day = Date of assessment (or event) - (Date of randomization).

For visit (or event) at or after randomization,

Study day = Date of assessment (or event) - (Date of randomization) + 1.

In case that the event date is partial or missing, the date will appear partial or missing in the listings. Study day will be calculated after imputation has been carried out as described in Appendix 2 Partial Date Conventions.

4.2.4 Baseline Measurements

For efficacy analyses, the baseline value is defined as the last non-missing measurement value prior to the randomization.

For safety analyses, the baseline value is defined as the last non-missing measurement collected on or before first study drug administration. However, if there is evidence that measurements are taken on the same day as administration of first IP, then a value taken strictly prior to the time of study drug administration or previous day(s) (closest to first study drug administration) will be used as baseline value.

[name] S.A Protocol RI-01-006

Statistical Analysis Plan

4.2.5 Treatment periods

Treatment periods are defined as:

- Induction Treatment Period (Week 1 to Week 4): (End date of Week 4 Start date of Week 1) +1
- Maintenance Treatment Period (Week 12 to Week 36): (End date of last available visit in maintenance period /Week 36 Start date of Week 12) +1, data as available for the subject who are still in the study.

4.2.6 Visit windowing

Nominal Visit will be used as collected in eCRF pages, except for vital signs. No visit window will be applied for other safety assessments. Study visits will be labelled as Screening, Induction Period- Baseline (Day 0), Week 2 (Day 8), Week 3 (Day 15), Week 4 (Day 22), Week 8, maintenance Period- Week 12, 20, 28 and 36, Follow-up period- Week 44, Week 52 (EOS/ET). For the subjects who prematurely discontinue the study prior to Week 52, their EOS/ET visit will be mapped to the correct visit based on target day.

Unscheduled Visits and Multiple Assessments

In general, unscheduled and retest (except for vital signs assessment) safety measurements will not be included in the by-visit summaries. Listings will include all scheduled, unscheduled, retest and early discontinuation data with the nominal visit originally recorded on the eCRF.

For vital signs since the assessments are being collected at every 30 minutes (± 5 minutes) during the course of the treatment administration and at end of infusion or more frequently as necessary, the summaries will be provided for each of timepoint available with in a visit for all the subjects. Difference between infusion start date/time to vital sign assessment date/time will be calculated and duration will be rounded to 0 min, 30 min, 60 min, etc. It is possible that multiple assessments of a subjects fall into the same visit-window of a timepoint, then the assessment closest to the target timepoint will be selected and rounded.

For tables displaying the worst-case scenario, such as shift tables or notable abnormalities, all assessments including unscheduled assessment will be used to identify the worst (e.g. the maximum or the minimum depending on parameter). Where applicable it will be defined for each parameter what the worst case is.

4.2.8 Common Calculations

For quantitative measurements, changes from baseline at Visit will be calculated as follows:

- Change at Visit = Measurement value at Visit Baseline Value (Baseline)
- Changes from baseline in categorical data will be summarized using shift tables, where appropriate.

Durations (excluding treatment duration) are calculated as:

- Duration (days) = End Date Start Date + 1
- Duration (weeks) = (End Date Start Date + 1) / 7
- Duration (months) = (End Date Start Date + 1) / 30.44.

4.2.9 Other Considerations

In general, listings will be sorted and presented by treatment group and subject number across all sites.

Confidence intervals (CIs), two-sided 95% for EMA and two-sided 90% for FDA, will be presented to one more decimal place than the raw data.

4.3 Software

All tables, figures and listings for Clinical Study Report (CSR) will be produced using SAS[®] version 9.4 (or a later version) in a secure and validated statistical computing environment. The version of SAS[®] actually used for the analysis will be noted in the CSR.

4.4 Analysis Sets

4.4.1 Intention-To-Treat Analysis Set

The Intention-To-Treat (ITT) Analysis Set will include all randomized subjects. The primary efficacy analysis will be based on the ITT Analysis Set.

If a subject received incorrect study drug, i.e., study drug different to the one assigned per the randomization list, the subject will be summarized and analyzed for the study treatment group per the randomization list. If a subject's stratum has been entered incorrectly in the randomization system, i.e., conflicting with the data in the clinical database, the stratum entered in the randomization system will be used for summaries and analyses.

4.4.2 Per-Protocol Analysis Set

The Per-Protocol Analysis Set (PPS) will include all randomized subjects who

- received at least one dose of study drug (sufficient compliance as defined in Section 4.9)
- have measurable disease at Baseline as confirmed by central review
- have an at least one available valid response evaluation up to Week 28 (\pm 4 weeks)
- and no major protocol deviations (such as administration of a forbidden treatment) that would significantly impact the primary efficacy endpoint (if, however, the forbidden treatment was administered due to PD, the subject will be included in the PPS as a non-responder).

[name] S.A	
Protocol RI-01-006	

Subjects will be considered to have a valid response evaluation if all required tests in accordance with published response criteria¹³ are available and have been obtained within \pm 4 weeks of the scheduled date, and the central imaging reviewers consider all imaging at Week 12 and Week 28 as properly evaluable for size comparison with the baseline images, and subjects have not received forbidden medications or other treatments for LTB-FL.

Final composition of the PPS will be determined prior to unblinding.

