6.7 Concomitant Therapy

Medications that are considered necessary for the subject's safety and well-being may be given during the course of the study at the discretion of the Investigator and must be recorded in the appropriate sections of the eCRF.

All medications taken by a subject within 1 month prior to screening are regarded as **prior medication** and must be documented as such in the eCRF.

All medications still being taken by a subject at the time of signing the Informed Consent Form (ICF) and which continue to be taken during the study, as well as all medications started after signing of the ICF, are regarded as **concomitant medication** and must be documented as such in the eCRF. The use of concomitant therapy, including prescription and non-prescription drugs, non-drug therapy, and dietary supplements and herbal preparations, is permitted as appropriate to treat AE or co-morbid conditions. Concomitant administration of any other experimental drug or a concomitant chemotherapy, anticancer hormonal therapy, radiotherapy, or immunotherapy is prohibited during study participation. This includes administration of rituximab not included in the protocol-defined treatment. If a subject requires tumour targeting treatment for FL other than the protocol-defined treatment with rituximab monotherapy, including, but not restricted to, other immunotherapies, chemotherapy, and radiotherapy, this will be defined as disease progression. The date the concomitant treatment was initiated will be collected in the eCRF.

Any other medication or vaccine (including over-the-counter or prescription medicines, vitamins, and/or herbal supplements) that the subject is receiving at the time of enrolment or receives during the study must be recorded along with:

- reason for use
- dates of administration including start and end dates
- dosage information including dose and frequency

The MM should be contacted if there are any questions regarding concomitant or prior therapy.

During their participation in the study, subjects should not take any prescription or non-prescription drug without the permission of the Study Investigator. However, the permission of the Study Investigator should be waived for medical emergencies.

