9.3.2 Per Protocol Population

The PP Population will include all subjects who are randomised into the study, receive at least one dose of study drug (sufficient compliance to be evaluated under blind conditions), have measurable disease at Baseline as confirmed by central review, have an at least one available valid response evaluation up to 7 months (\pm 4 weeks), and no major protocol deviations (such as administration of a forbidden treatment) that would significantly impact the primary efficacy endpoint. If the forbidden treatment was administered due to PD, the subject will be included in the PP Population as a non-responder. In the EMA analysis, both ITT and PP population will be considered as primary.

Subjects will be considered to have a valid response evaluation if all required tests in accordance with published response criteria¹³ are available and have been obtained within \pm 28 days of the scheduled date, and the central imaging reviewers consider all imaging at 3 months (Week 12) and 7 months (Week 28) as properly evaluable for size comparison with the baseline images, and subjects have not received forbidden medications or other treatments for LTB-FL.

Analysis of the PP Population may allow easier detection of any differences in treatment since the population includes only subjects who adhere to the protocol. Identification of the PP Population will be determined at one or several blinded data review meetings prior to unblinding.

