3.2 Definition of Endpoints / Variables

3.2.1 Definition of Efficacy Endpoints / Variables

3.2.1.1 Definition of the Primary Efficacy Endpoint / Variable

BOR up to Week 28 is defined as the best overall response at any radiologic tumor evaluations (based on central radiology review applying the Cheson 1999² response criteria for malignant lymphoma) up to the end of the allowed window for the Week 28 evaluations. Unscheduled and early termination evaluations will be only considered if they are complete and performed up to the end of the allowed window for the Week 28 evaluations.

[name] S.A	
Protocol RI-01-006	

The primary efficacy endpoint used in the statistical analysis is a binary (response / non-response) BOR up to Week 28 version is defined below. The impact of Intercurrent Events on binary BOR up to Week 28 is not described here but in Section 4.10.2.

For subjects with known tumor response at both Week 12 and Week 28, the definition of binary version of BOR up to Week 28 (the primary efficacy endpoint in the statistical analysis) is:

Response at Week 12	Response at Week 28	Binary version of BOR up to Week 28
CR, CRu or PR	Any known	Response
Any Known	CR, CRu or PR	Response
SD or PD	SD or PD	Non-Response

For subjects with a missing / unknown ("unknown" covers "not evaluable", "not available", "subject not anymore in the study", etc.) tumor response at Week 12 or at Week 28 and tumor response known at the other time-point, the definition of binary version of BOR up to Week 28 is:

Response at Week 12	Response at Week 28	Binary version of BOR up to Week 28
CR, CRu or PR	Missing / Unknown	Response
Missing / Unknown	CR, CRu or PR	Response
SD or PD	Missing / Unknown	Non-Response
Missing / Unknown	SD or PD	Non-Response

For subjects with only missing / unknown tumor responses, the definition of binary version of BOR up to Week 28 is:

Response at Week 12	Response at Week 28	Binary version of BOR up to Week 28
Missing / Unknown	Missing / Unknown	• Non-Response for main analysis using the exact score method, sensitivity analysis using stratified Mantel- Haenszel method, and FDA main estimand
		• Missing for sensitivity analyses within the estimand framework (except FDA main estimand) using multiple imputation approaches and for supplementary analyses as described in Section 4.10.2.3

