4.10.2 Analysis of the Primary Efficacy Endpoint / Variable

4.10.2.1 Main Analysis of the Primary Efficacy Endpoint / Variable

The main analysis will be performed for the ITT Analysis Set and the primary efficacy endpoint / variable (BOR up to Week 28) is defined in Section 3.2.1.1 (with non-response for subjects without any valid post-baseline tumor assessment up to Week 28).

Statistical hypotheses

With

 $\pi_{\text{DRL}_{\text{RI}}}$ denoting the true probability for BOR up to Week 28 in the DRL_RI treatment group

 $\pi_{MabThera^{(B)}}$ denoting the true probability for BOR up to Week 28 in the MabThera[®] treatment group

and $\delta = \pi_{\text{DRL}_\text{RI}} - \pi_{\text{MabThera}^{\circledast}}$ denoting the BOR up to Week 28 probability difference, the null hypothesis is

 $H_0: |\delta| \ge 0.17,$

verbally: DRL_RI is not biosimilar (is either inferior or superior) to MabThera[®] applying pre-specified symmetrical biosimilar margins $\pm 0.17 (\pm 17\%)$.

The alternative hypothesis is

 $H_A: |\delta| < 0.17,$

verbally: DRL_RI is biosimilar (is neither inferior nor superior) to MabThera[®] applying pre-specified symmetrical biosimilar margins $\pm 0.17 (\pm 17\%)$.

Statistical analysis method

Two-sided 90% and 95% CIs for the BOR up to Week 28 probability difference ((DRL_RI minus MabThera®) will be obtained by the unstratified exact score method (Chan 1999⁹) implemented in SAS Proc FREQ.

For FDA, biosimilarity will be concluded (i.e., the null hypothesis rejected) if the 90% CI is completely contained within the pre-defined interval (-0.17, 0.17).

For EMA, biosimilarity will be concluded (i.e., the null hypothesis rejected) if the 95% CI is completely contained within the pre-defined interval (-0.17, 0.17).

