4.10.2.2.2 Intercurrent Events

Table 1 and Table 2 lists the intercurrent events (ICEs) identified as relevant for BOR up to Week 28 for FDA and EMA respectively.

Table 1 Intercurrent Events for FDA

Intercurrent Event for FDA

Death prior to first post-baseline radiologic tumor examination

Missing scheduled post-baseline radiologic tumor examination up to Week 28 (for reason other than death)

- reason not related to COVID-19 pandemic
- reason related to COVID-19 pandemic

Initiation of forbidden treatment for LTB-FL prior to Week 28 radiologic tumor examination

Concomitant administration of any other experimental drug or a concomitant chemotherapy, anticancer hormonal therapy, radiotherapy, or immunotherapy is prohibited during study participation. This includes administration of rituximab not included in the protocol scheduled treatment. The relevant eCRF data will be reviewed by medical experts to identify forbidden treatments per the above definition. The programming team will use that information to derive the forbidden treatment ICE.

Table 2 Intercurrent Events for EMA

Intercurrent Event for EMA

Death prior to first post-baseline radiologic tumor examination

- reason for death known to be other than progressive disease
- reason for death progressive disease or unknown

Discontinuation of study treatment prior to first post-baseline radiologic tumor examination

- reason not related to COVID-19 pandemic
- reason related to COVID-19 pandemic

[name] S.A Protocol RI-01-006

Statistical Analysis Plan

Intercurrent Event for EMA

Missed or delayed study drug administration prior to Week 28 radiologic tumor examination

- reason not related to COVID-19 pandemic
- reason related to COVID-19 pandemic

Missing scheduled post-baseline radiologic tumor examination up to Week 28 (for reason other than death)

- reason not related to COVID-19 pandemic
- reason related to COVID-19 pandemic

Initiation of forbidden treatment for LTB-FL prior to Week 28 radiologic tumor examination

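### The per-protocol rule for forbidden treatment given because of progression ignores a response already documented, so a Week 12 responder can be Response in ITT and Non-response in PP

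*SAP*

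**What the plan says.** **Endpoint.** SAP 3.2.1.1 states: "BOR up to Week 28 is defined as the best overall response at any radiologic tumor evaluations", read centrally, up to the end of the Week 28 window. Its tables give Response for CR, CRu or PR at Week 12 combined with any known Week 28 result, and also when Week 28 is missing. PD at Week 28 does not undo a Week 12 response. On intercurrent events the section says: "The impact of Intercurrent Events on binary BOR up to Week 28 is not described here but in Section 4.10.2".

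**ITT main analysis.** SAP 4.10.2.1 applies that endpoint to all randomised subjects. The only override it states is "with non-response for subjects without any valid post-baseline tumor assessment up to Week 28".

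**PP analysis.** SAP 4.10.2.3.2 repeats the main analysis and the stratified Mantel-Haenszel analysis (4.10.2.2.1) on the PPS.

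**PP rule.** SAP 4.4.2 excludes subjects with major deviations "that would significantly impact the primary efficacy endpoint", naming forbidden treatment as its example, and then makes an exception: "if, however, the forbidden treatment was administered due to PD, the subject will be included in the PPS as a non-responder". Protocol 9.3.2 has the rule as a separate sentence: "If the forbidden treatment was administered due to PD, the subject will be included in the PP Population as a non-responder". Both sections also require, for a valid response evaluation, that the subject has received no forbidden medication or other treatment for the lymphoma.

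**Status of PP.** Protocol 9.3.2 makes ITT and PP both primary in the EMA analysis. SAP 4.10.2.3 lists the PPS analyses as supplementary, and SAP 4.14 does not record this as a change.

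**The concern.** ITT and PP should put the same endpoint to two populations. Here the PP rule replaces the endpoint value for some subjects, so a gap between the two results could come from scoring and not from adherence.

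The trigger also lies outside the centrally read endpoint. Study drug is stopped on investigator-assessed progression (protocol 7.2). Under protocol 6.7, a need for other tumour-targeting treatment, "including, but not restricted to, other immunotherapies, chemotherapy, and radiotherapy, this will be defined as disease progression". A local treatment decision can therefore cancel a response that central review has already recorded. If PP is primary for EMA, this enters an analysis on which equivalence is decided.

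The likely origin is visible in the Amendment 4 summary of changes. The endpoint moved from response at Week 28 to best response up to Week 28. The PP evaluability wording was adapted to this, while the non-responder sentence is the same in both columns. The sentence suited the former endpoint: a subject who had progressed and been treated by Week 28 was not a Week 28 responder.

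**Working it through.** The plan attaches no figure to this rule, so there is none to reproduce. The check is a comparison of the scoring rules, followed by a sense of scale.

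**1. Scoring side by side**

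| Course of subject | ITT main and Mantel-Haenszel (3.2.1.1) | Same analyses on PPS (4.4.2 rule) |
|---|---|---|
| PR at Week 12, then PD and forbidden treatment at Week 20; Week 28 PD or missing | Response | Non-response |
| PR at Week 12, PD at Week 28, no new treatment | Response | Response |
| SD at Week 12, then PD and forbidden treatment at Week 20; Week 28 PD or missing | Non-response | Non-response |

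Only the first row conflicts. It differs from the second because new treatment was started.

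**2. Effect per subject.** SAP 4.13.2 gives 156 per group. The PP set will be smaller, but its size is unknown, so 156 is used throughout. One re-scored subject moves the arm's rate by 1/156 = 0.64 points.

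**3. Plausible number affected.** The documents give no count. Protocol 2.2.3 reports 88% not needing new treatment at 3 years on induction plus maintenance in the cited watch-and-wait trial. Assuming a constant hazard:
- hazard = −ln(0.88)/36 = 0.00355 per month
- Weeks 12 to 28 = 16 weeks, about 3.7 months
- expected proportion ≈ 0.00355 × 3.7 = 1.3%
- expected number ≈ 0.013 × 156 = 2 per arm.

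This includes non-responders, so Week 12 responders should be fewer. Against that, new therapy in the cited trial meant chemotherapy or radiotherapy, and the forbidden list here is wider.

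**4. Effect on the interval.** Illustration with 88% in both arms (137/156; 88% is the expected reference rate in SAP 4.10.2.3.4), using Miettinen-Nurminen score intervals as a stand-in for the planned exact score interval:
- No re-scoring: 95% CI ±7.4 points. The simple formula gives a similar figure: 1.96 × √(2 × 0.88 × 0.12/156) = 7.2 points.
- Two re-scored in each arm: ±7.7 points. Five in each arm: ±8.1 points.
- Two re-scored in the DRL_RI arm only: difference −1.3 points, 95% CI −8.9 to +6.3.

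**5. Re-scored subjects, all in the DRL_RI arm, needed to take the lower limit past −17 points**

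| ITT difference before re-scoring | 95% CI, reference rate 88% | 90% CI, reference rate 88% | 95% CI, reference rate 80% |
|---|---|---|---|
| 0 | 14 | 16 | 12 |
| about −5 points | 6 | 8 | 4 |
| about −7 points | 3 | 5 | 1 |

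The 95% columns matter for EMA, where PP is primary under the protocol.

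**The case against.** The best defence is the qualifier in SAP 4.4.2. The rule sits in a clause about deviations that would significantly affect the primary endpoint. If a response is already on record at Week 12, later treatment cannot change best response, so it could be argued that the deviation does not qualify and the exception is never reached. ITT and PPS would then agree. This reading is strained. The SAP names forbidden treatment as its own example of an impacting deviation, and the protocol states the non-responder rule as a separate sentence. A co-primary analysis should not rest on a choice between the two readings.

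The qualifier does limit the point in one respect. The PP rule carries no date, whereas the intercurrent-event tables in SAP 4.10.2.2.2 restrict the same event to "Initiation of forbidden treatment for LTB-FL prior to Week 28 radiologic tumor examination". A reader might infer that a subject with PR at Weeks 12 and 28 who is treated for progression at Week 40 also becomes a non-responder. The documents do not support that. The parent clause concerns impact on the primary endpoint, SAP 4.5 ties major deviations to best response up to Week 28, and the Week 28 report uses data up to Week 28 ±7 days (SAP section 1). What stands is that the limit is implied, not written.

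A further defence is that scoring non-response is deliberately conservative. In an equivalence test it is not reliably so, since it can widen or narrow the observed difference depending on the arm. If it were intended, the ITT analysis should use it too.

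Finally, the handling of forbidden treatment in the estimand analyses is redacted. A reader might extend the conflict to those analyses. Nothing can be said about them either way.

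**Conclusion.** The inconsistency is real and can be read from the text. For a Week 12 responder given forbidden treatment because of progression before Week 28, the ITT main and Mantel-Haenszel analyses and their PPS counterparts use opposite values of one endpoint.

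Its numerical effect is probably small: about 2 or fewer subjects per arm, or at most about 1.3 points on an arm's rate (2/156). This rests on a constant hazard, the cited trial's figure and 156 per arm in PP. Near-equal numbers in the two arms hardly move the interval. A reader might infer from the last table that the rule could readily overturn the result. The documents do not support that: from equal rates of 88% it would take 14 subjects, all in one arm. It could matter only with an uneven split and a result already near the margin.

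The importance also depends on the status of PP, on which the protocol (primary for EMA) and the SAP (supplementary) disagree. The correction should be made because the stated rule misclassifies the endpoint and is cheap to repair. No sample size, margin or confidence level changes.

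**What to change.** Before unblinding, in both SAP 4.4.2 and protocol 9.3.2:

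1. Replace the non-responder sentence with: *Subjects given forbidden treatment because of PD before the Week 28 tumour examination remain in the PPS and are scored by SAP 3.2.1.1 on central assessments obtained before that treatment started; they are non-responders only if none of these shows CR, CRu or PR.* This also writes in the date limit that the intercurrent-event tables already use.
2. Amend the valid-response-evaluation sentence so that it bars only evaluations made after forbidden treatment started. Otherwise these subjects could still fail entry to the set that the first sentence keeps them in.

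Record the change in SAP 4.14, and reconcile there or in the protocol whether PP is primary or supplementary for EMA.

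With these changes a response documented before the forbidden treatment counts in both sets. A subject whose only response follows the forbidden treatment would still differ between ITT and PPS, but that difference does reflect adherence.

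The cost is two sentences in each document and the 4.14 entry. No new data are needed, because protocol 6.7 already collects the start date of such treatment. PP response rates may rise slightly.

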- 2. Clinical assessments will include the following: Physical examination (at the discretion of the Investigator), vital signs measurement (seated blood pressure, heart rate, respiration rate, and oral, axillary, or tympanic body temperature).
- 3. ECOG performance status.
- 4. Clinical laboratory tests: Blood and urine samples will be taken for haematology, biochemistry, coagulation, urinalysis, and pregnancy tests.

- 5. Serum LDH and β -2 microglobulin evaluation.
- 6. Samples for BAb and NAb will be obtained.
- 7. Assess AEs.
- 8. Review concomitant medications.

Maintenance Treatment Period (Week 12 to Week 36 ± 7 days)

Subjects will attend the study visit at Week 12 ± 7 days, and thereafter every 8 weeks (± 7 days) until Week 36. The subjects will attend the study site preferably from the morning until approximately mid-afternoon.

The procedures and assessments for the Maintenance Treatment Period are as follows:

- 1. Completion of a COVID-19 related screening questionnaire.
- 2. Clinical assessments will include the following: Physical examination (at the discretion of the Investigator, but including weight), vital signs measurement (blood pressure, heart rate, respiration rate, and oral, axillary, or tympanic body temperature).
- 3. ECOG performance status assessments.
- 4. Urine or serum pregnancy test (performed locally, according to local practice).
- 5. Clinical laboratory tests: Blood and urine samples will be taken for haematology, biochemistry, coagulation, and urinalysis.
- 6. At Week 28 Only: Samples for BAb and NAb will be obtained before the infusion of study drug.
- 7. Serum LDH and β -2 microglobulin evaluation.
- 8. Viral disease screening: HBV DNA (as applicable) and HCV RNA (as applicable).
- 9. At Week 12 and 28 only (Month 3 and Month 7, i.e. 2 and 6 months after completion of rituximab induction) tumour assessments (using a CT scan and, where available according to study site standard of care, a [¹⁸F]FDG-PET or PET-CT scan) based on central radiology review in accordance with the response criteria for malignant lymphoma.¹³ Subjects who have withdrawn from study drug for any reason other than disease progression will also undergo tumour assessment at Week 28.

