9.3 Populations for Analyses

9.3.1 Intent to Treat Population

The Intent to Treat (ITT) Population will include all randomised subjects. The primary efficacy analysis will be based on the ITT Population.

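### Protocol 9.3.2 makes the per-protocol set co-primary for EMA, the SAP treats it as supplementary without recording a change, and the rules for who belongs to the set conflict

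*SAP*

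**What the plan says.** **Role of the set.** Protocol 9.3.1 states: "The primary efficacy analysis will be based on the ITT Population". Protocol 9.3.2 then adds a sentence specific to one agency: "In the EMA analysis, both ITT and PP population will be considered as primary". SAP 4.10.2.1 performs the main analysis on the ITT set and states both agency rules there: 90% CI for FDA and 95% CI for EMA, each inside (-0.17, 0.17). SAP 4.10.2.3.2 repeats the main and stratified analyses on the PPS, under the heading for supplementary analyses. SAP 4.14, which lists changes from the protocol, covers the AUEC model and the intercurrent events but not the role of the PPS. The SAP cites protocol version 5.0 as its basis.

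**Membership.** SAP 4.4.2 and protocol 9.3.2 share these elements:

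- Subjects must "have an at least one available valid response evaluation up to Week 28" (SAP wording).
- An evaluation is valid only if "the central imaging reviewers consider all imaging at Week 12 and Week 28 as properly evaluable for size comparison with the baseline images" and, further, "and subjects have not received forbidden medications or other treatments for LTB-FL". The protocol has the same imaging condition: reviewers "consider all imaging at 3 months (Week 12) and 7 months (Week 28) as properly evaluable".
- Major deviations exclude a subject when they would significantly affect the primary endpoint. If a forbidden treatment was given because of PD, however, "the subject will be included in the PPS as a non-responder".

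SAP 4.5 defines major deviations more widely, to include those touching a subject's rights, safety or well-being. It excludes subjects with major deviations from the PPS without the endpoint limit. For detail it refers to a separate deviation specification.

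**The concern.** A statistician who follows the SAP would declare equivalence for EMA on ITT alone. One who follows the protocol would treat the PPS as carrying equal weight. Nothing says whether EMA success needs one set or both, and the SAP does not record that it has moved away from the protocol.

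The PPS itself cannot be built unambiguously either. Two teams working from the same text could reach different lists, for three reasons: which major deviations exclude, whether subjects treated for progression are in or out, and whether one evaluable scan is enough. Deciding membership before unblinding prevents choices driven by treatment, but it does not tell the review meeting which rule to apply.

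If both sets must pass for EMA, the size and make-up of the PPS affect the power of the EMA analysis. If the PPS is only a check, its value depends on exclusions not being tied to outcome.

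**Working it through.** **1. Role of the PPS.** Protocol 9.3.1 makes ITT primary in general; 9.3.2 adds PP as primary for EMA. The two protocol sentences are compatible. The SAP keeps the first and not the second. No multiplicity issue arises from requiring both sets, since that is a stricter rule.

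**2. Deviations.**

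| Text | Which major deviations exclude |
|---|---|
| Protocol 9.3.2, SAP 4.4.2 | those with a significant effect on the primary endpoint |
| SAP 4.5 | all, including those affecting only rights, safety or well-being |

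A subject whose only major deviation concerns, say, consent procedure stays in under the first row and leaves under the second.

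**3. Forbidden treatment for PD.** The fourth bullet of SAP 4.4.2 includes this subject as a non-responder. The validity paragraph gives no PD exception, and a valid evaluation is a condition of entry, so the same subject fails it. Protocol 6.7 defines needing other tumour-targeting treatment for FL as disease progression, so the two rules meet on the same people.

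**4. One scan or two.** SAP 3.2.1.1 classifies a subject from one known time point. If the validity clause means both visits must have evaluable scans, two groups that 3.2.1.1 classifies would leave the PPS: Week 12 responders who miss Week 28, and early progressors with no scheduled Week 28 scan. On the latter, protocol 8.1.2 says: "Subjects who have withdrawn from study drug for any reason other than disease progression will also undergo tumour assessment at Week 28". Progressors have an ET visit 8 weeks (56 days) after the last dose (protocol 4.5). Against the SAP Appendix 5 windows (Week 12: Days 56–112; Week 28: Days 168–224):

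- last dose Day 22: 22 + 56 = Day 78, in the Week 12 window only
- last dose Week 12: 84 + 56 = Day 140, in neither window
- last dose Week 20: 140 + 56 = Day 196, in the Week 28 window

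**5. Power if both sets must pass (illustration).** From the SAP: 156 per arm, margin 0.17, 95% CI. Assumed: reference rate 80%, true difference 0, share f of non-responders and g of responders dropped, equal in both arms. The documents give no drop rates. The only reference rate they show is the 88% in SAP 4.10.2.3.4, so that is run too.

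Approximate power for one set with n per arm and rate p: SE = √(2p(1−p)/n); power = 2Φ(0.17/SE − 1.96) − 1.

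- Nobody dropped: SE = √(0.32/156) = 0.0453; 0.17/SE = 3.753; power 92.7%.
- f = g = 10%: n = 140.4, SE = 0.0477; 0.17/SE = 3.561; PPS power 89.1%.
- f = 10%, g = 20%: retained share 0.80×0.80 + 0.20×0.90 = 0.82, n = 127.9, p = 0.64/0.82 = 0.780; SE = 0.0518; 0.17/SE = 3.285; PPS power 81.5%.

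The joint figure needs the correlation between the sets. It comes from 400,000 simulated trials per scenario, using a score test as a stand-in for the exact score interval:

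| f, g | Joint power, reference 80% | Joint power, reference 88% |
|---|---|---|
| 0, 0 | 92.5% | 98.9% |
| 10%, 0 | 91.4% | 98.7% |
| 10%, 5% | 89.9% | 98.4% |
| 10%, 10% | 87.8% | 97.7% |
| 10%, 20% | 80.9% | 94.6% |

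In the last row about 156×(0.80×0.20 + 0.20×0.10) = 28 of 156 leave the reference arm at an 80% rate.

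**6. False passes if both sets must pass.** At a true difference of −17 points and an 80% reference rate, the joint false-pass rate is 2.6% with nobody dropped, 2.2% at f = 10%, g = 0, and 1.3% at f = 10%, g = 20%. It does not rise.

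**The case against.** **The imaging clause is not a contradiction.** A reader might infer that the definition demands two evaluable scans and so cancels its own entry rule. The documents do not support that. Reviewers can only judge images that exist; the same sentence refers to a single scheduled date; and a two-scan reading would empty the at-least-one condition of meaning. Reading the clause as imaging obtained reconciles the text. On that reading most early progressors stay in: an ET scan at Day 78 counts for Week 12, and a subject last dosed at Week 12 reached the visit where that scan is due. What stands is that neither document says which reading applies.

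**The PPS cannot pass a non-equivalent product on its own.** A reader might infer that dropping non-responders inflates the EMA error rate. No document lets the PPS decide alone, and under a both-sets rule the false-pass rate falls or stays level. Selective dropping would only weaken the PPS as a check on ITT.

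**The forbidden-treatment bullet is specific.** It names both membership and outcome, so a specific-over-general reading favours it. That is the likely intent, but the validity clause still lacks the exception.

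**The deviation specification may narrow SAP 4.5.** It is not among the documents, so the practical width is unknown. The visible texts still differ.

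**No EMA result is lost.** SAP 4.10.2.3.2 produces the PPS interval anyway, and the worst joint power shown stays above the 80% target in SAP 4.13.2. Both are true. The gap is in the status of the result and the decision rule. Parts of protocol 9.4.1.1 and the SAP estimand sections are redacted and may say more, but they do not undo the visible supplementary heading.

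**Conclusion.** The point holds as three conflicts in current text: the role of the PPS for EMA, the breadth of the deviation exclusion, and the treatment of subjects given forbidden therapy for progression. The first matters most, because following the SAP as written would draw the EMA conclusion on a different basis from the protocol. The one-scan-or-two question is an ambiguity of lesser weight.

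The ITT main analysis and the FDA conclusion are untouched. The cost falls on the clarity of the EMA rule, on the PPS as a check, and on EMA power if both sets must pass: a loss of about 5 points when 10% of all subjects are dropped, and of about 12 points in the heaviest case shown, at an assumed 80% reference rate. At 88% the losses are about 1 and 4 points. These sizes rest on assumed drop rates, no true difference and equal dropping in both arms; they show scale and are not forecasts. It should be fixed, and wording is enough.

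**What to change.** Before the blinded data review:

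1. In SAP 4.10.2.1 and 4.10.2.3.2, make the PPS co-primary for EMA as protocol 9.3.2 says, requiring the 95% CI inside (-17%, 17%) in both ITT and PPS. Otherwise, record and justify the departure in SAP 4.14.
2. Limit the SAP 4.5 exclusion to major deviations that significantly affect the primary endpoint, matching SAP 4.4.2 and protocol 9.3.2.
3. Add the PD exception to the forbidden-treatment part of the validity clause. State also whether the PPS non-responder rule overrides the SAP 3.2.1.1 table for a Week 12 responder later given forbidden treatment for PD, since the table alone would call that subject a responder.
4. State that validity is judged per time point: one centrally evaluable post-baseline assessment in the Week 12 or Week 28 window is enough, counting complete ET and unscheduled scans as SAP 3.2.1.1 does.

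The cost is SAP wording and a matching protocol clarification; no further data are needed. The downside is that the PPS may be slightly larger and include subjects with only one evaluable scan.
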